### **9.7.2.2 Overall Survival**

OS is defined as the time interval from first treatment to death of any cause. Subjects who are alive will be censored at the last known date subject is alive. The 12-month OS rate and the product-limit estimate of median survival, as well as their 90% confidence intervals will be summarized. A Kaplan-Meier curve will summarize OS graphically. The 18-month and 24-month survival rates will also be provided along with their 90% CIs.

### **9.7.2.3 Duration of Response**

Duration of response is defined as the time from response (CR or PR, whichever occurs first) to investigator assessed progression using RECIST 1.1 or death, and will be summarized based on

the number of subjects with response in the FAS. Subjects who do not have disease progression or have not died will be censored at the date when the last radiographic tumor assessment determines a lack of progression.

Duration of response will be summarized using the product-limit estimate of median survival along with its 90% confidence interval. The Kaplan-Meier curve will summarize duration of response graphically.

In case some additional immune-related responders are observed, duration of response analyses using iRECIST criteria will be provided. For subjects who are not evaluated by iRECIST criteria, their tumor response based on RECIST 1.1 response guidelines will be used.

### **9.7.3 Subgroup Analyses**

Each cohort will be analyzed individually for the efficacy endpoints as the background response rates are known to be different in each group. In addition, small sample size prevents further subgroup analyses from being possible.

## **9.8 Exploratory Analyses**

Analyses of exploratory endpoints will be based on the FAS, where both baseline and at least one post-baseline assessment are available. Missing data will not be imputed. Analyses will focus on comparing the post-baseline values with the baseline values. Correlation between tumor response and immune responses will be explored.

Continuous data will be summarized via mean (and 95% CI), standard deviation, median, minimum, and maximum by visit where samples are collected per trial schedule. In case of log-normal data, log transformations may be performed and summarized with the geometric means in place of the arithmetic means and 95% CIs.

## **9.9 Safety Analysis**

Safety will be monitored by performing physical examinations including vital signs, routine laboratory measurements, as well as by evaluating AEs. AEs will be followed as described in [Section 8](#) of this protocol.

Safety will be evaluated by the incidence of Treatment-Emergent Adverse Events (TEAEs) and SAEs, physical examination, laboratory abnormalities and percentage of subjects experiencing dose modifications, interruptions, and/or discontinuation, based on the FAS.

### **9.9.1 Adverse Events**

Adverse events will be recorded on the case report forms by the Investigator using verbatim terms that best describe the event. A TEAE is an adverse event with an onset on or after initiation of

trial product, or an adverse event present at initiation of trial product that worsens (*i.e.*, increase in severity: On-Study Grade > Baseline Grade; or relationship to trial product is reported as a possible, probable, or definite). Verbatim descriptions of TEAEs will be mapped to Medical Dictionary for Regulatory Affairs (MedDRA) Version 20 or newer and graded according to NCI-CTCAE, Version 5. All TEAEs (to include SAEs and AESIs) occurring from the first dose through 30 days of last dose of trial product, if unrelated to trial product or non-serious, and all trial product related SAEs and AESIs through 100 days of last dose of trial product, will be summarized by system organ class, and preferred term and further by NCI-CTCAE grade. On subject-based AE tables, for each specific TEAE, a subject will be counted only once under the maximum severity experienced. Similar summaries will be provided for all Grade 3 or higher TEAEs, SAEs, and AEs that lead to discontinuation of trial product. All AEs will be included in the subject listings. Separate listings of subjects that discontinue trial product due to an AE, and listings of subjects with SAEs and deaths will also be presented.

### **9.9.2 Laboratory Data**

Laboratory toxicities will be defined based on universal normal ranges and NCI-CTCAE, Version 5.0. The number and percentage of subjects will be summarized by grade using the most severe grade by cycle. Clinically significant changes in laboratory values will be summarized. Laboratory values will be listed, with Grade 3 or 4 values flagged.

### **9.9.3 Treatment Exposure**

Treatment exposure to CV301 in combination with atezolizumab will be provided. Number of CV301 injections and atezolizumab infusions administered, duration of exposure, and number of subjects with dose interruptions will be summarized based on the FAS.

### **Missing Data**

For duration of OS, PFS, or duration of response, subjects who are lost to FU will be analyzed as censored observations on the date of last known alive for OS, or last radiographic assessment for PFS and duration of response. Missing or partial dates will be imputed for prior/concomitant medications, adverse events, and cancer history. Details will be provided in the statistical analysis plan.

### **9.10 Multiplicity**

[figure not shown]
Due to the two-cohort, two-stage design of this Phase 2 trial, the primary endpoint of objective response rate will be tested multiple times. To account for this, the sample size for each cohort was based on a one-sided nominal alpha of 0.025 and 70% power. As each cohort represents an independent test, the overall trial-wide type I error rate would remain at or below 0.05 (one-sided). Based on simulations with the two-stage, two-cohort design, the overall type-1 error rate will be approximately 4.7%, and the power for the trial indicating at least one of the two cohorts will be positive given the alternative hypotheses are true, is approximately 91%.

## 9.11 Interim Analysis

Due to the two-stage design, an interim analysis with pre-specified stopping rules will be performed within each cohort. The ORR will be calculated after the first stage subject accrual is complete, separately for each cohort. Although the primary efficacy analysis will be performed on the FAS, if it is unclear within the first 14 FAS subjects in Cohort 1 (or 13 in Cohort 2) that the criteria are met for futility for Stage 1, enrollment will continue in the cohort until the full Stage 1 sample size is reached for the EE Set. If, even with enrolling additional subjects for the EE Set and those subjects all being responders, the cohort would not be able to reach the required number of responders to move to Stage 2, the cohort will be discontinued without reaching the full size of the EE Set.

The decision rules are as follows:

**Figure 1: Interim Analysis Decision Tree**

The decision to stop an individual cohort will be independent for each cohort.

## **9.12 Timing of Analyses**

The first post-treatment objective radiographic response assessment by the investigator will occur approximately 10 weeks after first treatment, with the second occurring 12 weeks later at the Week 22 visit. For subjects who have completed multiple scans, the best objective response will be used.

If at least 4 objective responses in Cohort 1 (or 3 objective responses in Cohort 2) are observed in the FAS prior to the end of Stage 1, enrollment of Stage 2 subjects will continue regardless of the full enrollment of the EE Set. If the results of Stage 1 are unclear based on full enrollment of Stage 1 in the FAS, enrollment will continue until the full Stage 1 sample size is reached for the EE Set. If success is not possible in Stage 1, even with continuing enrollment until the full EE set was reached and all additional subjects were responders, the cohort will be discontinued without meeting full enrollment of the EE Set. In addition, the timing of the initiation of Stage 2 in a cohort need not depend on the completion of Stage 1 in the opposite cohort.

The end of Stage 2 analyses will again be based on best objective response outcomes. If the required number of responses are observed for a positive outcome in Stage 2 for the FAS, enrollment will be stopped and the trial will be declared a success. If it is unclear if the study is successful based on the FAS subjects, additional subjects will be enrolled until the full sample size for Stage 2 is reached in the EE Set. Because objective radiographic response rates may increase with further follow up, the data may be analyzed with updates if subsequent follow up demonstrates additional objective responses.

Final analyses will occur when all subjects have either completed the 2-year treatment period, or have progressed.

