## 4 Trial Design

### 4.1 Experimental Design

This is a Phase 2, single-arm, multi-institutional clinical trial designed to study the combination of CV301 with atezolizumab in the first-line treatment of UC not eligible for cisplatin-containing chemotherapy (Cohort 1) and in the second-line treatment of UC previously treated with standard first-line cisplatin-based chemotherapy (Cohort 2). The trial will be performed using an optimal two-stage design within each cohort ([Simon, 1989](#)). For the purpose of this trial, subjects are considered enrolled once they have received their first dose of trial product.

Stage 1, Cohort 1: Enroll 14 subjects. If objective response is not achieved in at least four subjects, the cohort will be stopped for futility. If objective response is achieved in at least four subjects, the cohort will proceed to Stage 2.

Stage 1, Cohort 2: Enroll 13 subjects. If objective response is not achieved in at least three subjects, the cohort will be stopped for futility. If objective response is achieved in at least three subjects, the cohort will proceed to Stage 2.

Stage 2, Cohort 1: Enroll an additional 19 subjects, such that a total of 33 subjects are available for the primary endpoint analysis.

Stage 2, Cohort 2: Enroll an additional 22 subjects, such that a total of 35 subjects are available for the primary endpoint analysis.

Further details of the two-stage design are in [Section 9](#).

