2.6.4 Interim Analyses

The trial is designed using Simon's 2-stage design in 2 cohorts, number of subjects with objective responses will be continuously monitored with pre-specified efficacy-based stopping rules for each cohort. Although the primary efficacy analysis will be performed on the FAS, if it is unclear within the first 14 FAS subjects in Cohort 1 (or 13 in Cohort 2) that the criteria are met for futility for Stage 1, enrollment will continue in the cohort until the full Stage 1 sample size is reached for the EE Set. If, even with enrolling additional subjects for the EE Set and those subjects all being responders, the cohort would not be able to reach the required number of responders to move to Stage 2, the cohort will be discontinued without reaching the full size of the EE Set in Stage 1.

The decision rules are described in [Figure 1](#).

Figure 1. Interim Analysis Decision Tree

Any decisions made regarding continuation of the trial will happen for each cohort, individually.

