2.6.4.1 Primary Interim Analysis

The first post-treatment objective radiographic response assessment by the investigator will occur approximately 10 weeks after first treatment, with the second occurring 12 weeks later at the Week 22 visit. When the first 14 subjects in the FAS in Cohort 1, or the first 13 subjects in the FAS in Cohort 2 have completed at least 2 post-baseline CT scans (or MRIs if applicable), analysis for the FAS will be performed. If the number of responders meets the Stage 1 continuation criterion (> 3 responses for Cohort 1 or > 2 responses for Cohort 2), enrollment for the cohort will continue until the FAS has a total 33 subjects in Cohort 1, or 35 subjects in Cohort 2. Subjects who are enrolled to the EE set for the Stage 1 sensitivity analyses will be included as part of the total number of subjects in the FAS.

For subjects who have completed multiple scans, the best objective response will be used. Since the number of responders is continuously monitored, if the continuation criterion is met in either cohort in the FAS before the first 14 subjects in Cohort 1 and the first 13

subjects in Cohort 2 have completed at least 2 post-baseline tumor assessments, enrollment for the cohort will resume as described above.

If the number of responders does not meet the continuation criterion when the first 14 subjects in the FAS in Cohort 1, or the first 13 subjects in the FAS in Cohort 2, have completed at least 2 post-baseline tumor assessments, progress prior to having 2 post-baseline tumor assessments, or discontinue early from the trial, the combination treatment for the cohort will not be considered promising.

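### Protocol 9.12 ends Stage 2 enrolment on a response count, with no minimum sample size and at trial level, against the fixed 33/35 per cohort set elsewhere; the sentence needs rewording, but error rates are not affected

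*Protocol*

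**What the plan says.** Protocol 9.12 introduces the rule with "The end of Stage 2 analyses will again be based on best objective response outcomes". It then says that if the required number of responses is seen in the FAS, "enrollment will be stopped and the trial will be declared a success". If the result is unclear, "additional subjects will be enrolled until the full sample size for Stage 2 is reached in the EE Set".

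Other sections fix the Stage 2 size:

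- Protocol 4.1, Cohort 1: "Enroll an additional 19 subjects, such that a total of 33 subjects are available for the primary endpoint analysis".
- Protocol 4.1, Cohort 2: "Enroll an additional 22 subjects, such that a total of 35 subjects are available for the primary endpoint analysis".
- SAP 2.6.4.1, once Stage 1 is passed: "enrollment for the cohort will continue until the FAS has a total 33 subjects in Cohort 1, or 35 subjects in Cohort 2".
- SAP 4.1 ties the maximum of 33 or 35 to passing Stage 1 and to nothing else.
- SAP 4.4.5.1 tests at the end of Stage 1 and the end of Stage 2, within cohort. Success is 13 or more of 33, or 10 or more of 35. It resets the criterion if the set exceeds plan and has no provision for a shortfall.

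On decision level, the text with Protocol Figure 1 reads: "The decision to stop an individual cohort will be independent for each cohort". SAP 2.6.4 likewise decides cohort by cohort, and says that responder counts "will be continuously monitored with pre-specified efficacy-based stopping rules for each cohort". SAP 4.5 declares no departure from the protocol's analyses.

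**The concern.** The sentence in 9.12 is an enrolment and success rule. Taken by itself, it lets enrolment end at the 13th response in Cohort 1 or the 10th in Cohort 2, whatever number has been enrolled. The SAP contains no such rule, yet says that nothing was altered, so the two documents disagree without acknowledging it. The trial is open-label with investigator-assessed response, so the stopping point should not depend on an interpretation chosen after the counts are visible.

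At stake is estimation. The sample size would depend on the outcome, the ORR would rest on fewer subjects, and the figure quoted for a positive cohort would be somewhat higher than the planned design would give. The word trial is a separate defect, because success is otherwise judged by cohort.

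**Working it through.** **Inputs** (Protocol 1.4, 9.7.1; SAP 4.1). Cohort 1: n1 = 14, stop if 3 or fewer responses; n = 33, reject at R = 13; null ORR 0.23, alternative 0.43. Cohort 2: n1 = 13, stop if 2 or fewer; n = 35, R = 10; null 0.15, alternative 0.33. The interval is a two-sided 90% Clopper-Pearson (Protocol 9.7.1).

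**1. Reproduce the plan.** P(reject) = Σ over x > r1 of b(x; n1, p) · P(X2 ≥ R − x), with X2 ~ Bin(n − n1, p).

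| | Type I error | Power | Stated |
|---|---|---|---|
| Cohort 1 | 0.02437 | 0.70266 | 0.0244 / 0.7027 |
| Cohort 2 | 0.02494 | 0.70918 | 0.0249 / 0.7092 |

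**2. Literal rule, immediate read-out.** Follow each cohort subject by subject. Stop for futility at n1 if the count is r1 or less, stop for success when the count first reaches R, and otherwise stop at n. A count once reached cannot be lost, so a path that reaches R before n also has at least R at n. Type I error and power are therefore exactly those in step 1.

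**3. Effect on the estimate at the design alternatives.** With path probability w, count x and final size k: mean = Σ w·x/k; RMSE = √Σ w·(x/k − p)². Coverage is the total w of paths whose 90% interval contains p.

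| | Cohort 1, enrol to 33 | Cohort 1, literal | Cohort 2, enrol to 35 | Cohort 2, literal |
|---|---|---|---|---|
| Mean ORR, all outcomes | 0.418 | 0.432 | 0.312 | 0.330 |
| Bias against true ORR (points) | −1.2 | +0.2 | −1.8 | 0.0 |
| RMSE | 0.106 | 0.119 | 0.105 | 0.122 |
| Coverage of 90% interval | 92.0% | 91.2% | 90.9% | 90.9% |
| Mean n, successful cohorts | 33 | 27.0 | 35 | 26.6 |
| Successful cohorts stopping short | 0% | 93% | 0% | 96% |
| Mean ORR, successful cohorts | 47.15% | 49.15% | 36.49% | 39.06% |

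The difference given success is 49.15 − 47.15 = 2.0 points and 39.06 − 36.49 = 2.6 points.

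**4. Lag before read-out (assumed; accrual is not given).** If the R-th response occurs in subject k and L more subjects enrol before it is known, then m = min(L, n − k) and the expected ORR on that path is (R + m·p)/(k + m). The excess over full enrolment, given success, is:

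| L | Cohort 1 | Cohort 2 |
|---|---|---|
| 0 | +2.0 points | +2.6 points |
| 5 | +0.8 | +1.3 |
| 10 | +0.2 | +0.5 |

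**5. What a reader would see.** In Cohort 1, 13/33 is 39% (90% interval 25.1 to 55.2%), while 13/28 is 46% (30.1 to 63.4%). In Cohort 2, 10/35 is 29% (16.4 to 43.6%), while 10/29 is 34% (20.0 to 51.4%).

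**The case against.** The strongest reply is that the literal reading is not the intended one. The paragraph opens with the end-of-Stage-2 analysis, and the sentence after the rule is its alternative branch, the EE top-up. In sequence, the rule says that a positive FAS result at the end of Stage 2 makes the top-up unnecessary. This reading is at least as natural, and it agrees with every other section that fixes 33/35. It stands as a likely intention, but it is not written down.

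A reader might take the SAP's continuous monitoring as proof of a Stage 2 early-success rule. The documents do not support that. SAP 2.6.4 and 2.6.4.1 spell the monitoring out only for Stage 1, where reaching the count lets a cohort continue. The content of the Figure 1 decision tree could not be read and may clarify this further.

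A reader might also infer that the ORR is biased upward in general. It is not. Averaged over all outcomes at the design alternatives, early success stopping roughly cancels the downward bias from the futility stop. The 2.0 to 2.6 points arise only given success and relative to full enrolment.

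Finally, a reader might infer that one cohort's success closes the other. That would be costly: closing Cohort 2 at 25 or 30 subjects would cut its power from 0.709 to 0.29 or 0.53. But these closures are hypothetical. No text orders them, and both documents decide by cohort. What stands is loose wording.

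Immediate read-out is also unrealistic. Responses need confirmation at least 4 weeks later (Protocol Appendix 4), and scans fall at about Weeks 10 and 22 (Protocol 9.12), so the zero-lag figures are upper limits.

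**Conclusion.** The conflict in wording is real and should be corrected; the consequence is modest. As written, 9.12 permits an outcome-dependent Stage 2 size that Protocol 4.1 and the SAP do not, and it names the trial where the cohort is the decision unit. Even on the literal reading there is no inflation of type I error, no loss of power in a cohort that is allowed to run, and no interval coverage below nominal at the design alternatives. The cost is precision (RMSE up by about 0.013 in Cohort 1 and 0.017 in Cohort 2) and, for a successful cohort, an ORR at most 2.0 to 2.6 points above full enrolment. These figures assume the design alternatives, independent subjects and immediate read-out. The excess shrinks to 0.2 to 0.5 points with an assumed 10-subject lag. If the sentence only cancels the EE top-up, none of this arises.

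**What to change.** Replace the sentence in Protocol 9.12 with:

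> Each cohort that passes Stage 1 enrols to 33 (Cohort 1) or 35 (Cohort 2) FAS subjects regardless of when 13 or 10 responses are reached; if the criterion is then met in the FAS, that cohort is declared positive and no further subjects are enrolled for the EE Set. Success in one cohort does not stop the other.

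In SAP 2.6.4, state that continuous monitoring and the stopping rules apply to the Stage 1 decision only. If early success stopping is in fact wanted, put it in both documents with an estimator and interval suited to it.

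The cost is wording in two documents. Compared with literal early stopping at zero lag, a successful cohort would enrol on average about 6 more subjects in Cohort 1 (33 − 27.0) and about 8 more in Cohort 2 (35 − 26.6), never above the planned size.

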### 9.3 Analysis Populations

For the purpose of statistical analysis, there will be 2 analysis populations: Full Analysis Set (FAS) and the Efficacy Evaluable Set (EE).

The FAS consists of all subjects taking any amount of trial vaccine, whether MVA-BN-CV301 or FPV-CV301. The FAS will be the primary population for all analyses.

The EE Set consists of all subjects from the FAS who received 2 prime doses of MVA-BN-CV301 (Weeks 1 and 4).

The EE population will be used in sensitivity analyses for efficacy.

Subjects who failed to meet the EE Set criteria will be replaced unless 4 or more responses in Cohort 1 (or 3 or more responses in Cohort 2) have been observed for the FAS population, or the number of responders will still be less than 4 in Cohort 1 (or 3 in Cohort 2) even if all replacement subjects would be responders. If there are more than 14 evaluable subjects in Cohort 1 (or 13 in Cohort 2) at the end of Stage 1 analysis, or more than 33 in Cohort 1 (or 35 in Cohort 2) evaluable subjects at the end of Stage 2 analysis, primary evaluation will be based on the first 14 (or 13) accrued or first 33 (or 35) accrued FAS subjects.

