## **9.7 Efficacy Analysis**

### **9.7.1 Primary Efficacy Analysis**

The ORR is defined as the proportion of subjects with an objective tumor response (CR or PR) based on RECIST 1.1 evaluations as performed by the investigator. Based on prior published results with atezolizumab, the null ORR for Cohort 1 is 0.23, and for Cohort 2 is 0.15.

Cohort 1: In the first stage, 14 subjects will be accrued. If there are 3 or fewer responses in these 14 subjects, the cohort will be stopped. Otherwise, 19 additional subjects will be accrued for a total of 33. The null hypothesis will be rejected if 13 or more responses are observed in 33 subjects. This design yields an actual type I error rate of 0.0244 and power of 0.7027 when the true ORR is 0.43 for the combination.

Cohort 2: In the first stage, 13 subjects will be accrued. If there are 2 or fewer responses in these 13 subjects, the cohort will be stopped. Otherwise, 22 additional subjects will be accrued for a total of 35. The null hypothesis will be rejected if 10 or more responses are observed in 35 subjects. This design yields an actual type I error rate of 0.0249 and power of 0.7092 when the true ORR is 0.33 for the combination.

In the case that the number of responses required to move to Stage 2, individually per cohort, is met in the FAS population, the study will move to Stage 2 without enrolling the full EE Set. If Stage 1 results are not clear after enrolling the prescribed number of Stage 1 subjects in the FAS, enrollment will continue until the EE Set meets the prescribed number of Stage 1 subjects for the interim futility analysis. In the event continuing enrollment of the EE Set would still not produce a positive outcome for Stage 1, the cohort will be discontinued without meeting the full Stage 1 sample size for the EE set.

For the final primary efficacy analysis, the number and percent of subjects with OR, and in each category of objective tumor response, will be summarized based on the FAS. The two-sided 90% exact binomial confidence interval for the ORR will be calculated using the Clopper-Pearson method.

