2.1 Trial Description

This is a Phase 2, single-arm, multi-institutional clinical trial designed to study the combination of CV301 with atezolizumab in the first-line treatment of urothelial cancer (UC) not eligible for cisplatin-containing chemotherapy (Cohort 1), as well as in the second-line treatment of UC previously treated with standard first-line cisplatin-based chemotherapy (Cohort 2). The trial will be performed using an optimal two-stage design within each cohort (Simon, 1989). For the purpose of this trial, subjects are considered enrolled once they have received their first dose of trial product.

Stage 1, Cohort 1: Enroll 14 subjects. If objective response is not achieved in at least four subjects, the cohort will be stopped for futility. If objective response is achieved in at least four subjects, the cohort will proceed to Stage 2.

Stage 1, Cohort 2: Enroll 13 subjects. If objective response is not achieved in at least three subjects, the cohort will be stopped for futility. If objective response is achieved in at least three subjects, the cohort will proceed to Stage 2.

Stage 2, Cohort 1: Enroll an additional 19 subjects. If any subject is not evaluable for the primary endpoint, the subject may be replaced until a total of 33 subjects are evaluable for the primary endpoint of objective response rate (ORR).

Stage 2, Cohort 2: Enroll an additional 22 subjects. If any subject is not evaluable for the primary endpoint, the subject may be replaced until a total of 35 subjects are evaluable for the primary endpoint of ORR.

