4.1 Planned Sample Size

A Simon's two-stage Minimax design (Simon, 1989) was used to calculate sample size for Cohort 1. Cohort 1 will have a minimum of 14 subjects and a maximum of 33 subjects, with the maximum occurring if and only if at least 4 subjects have an objective response in the first stage of the trial. The alternative admissible 2-stage design (Jung et al., 2004) was used to calculate sample size for Cohort 2. Cohort 2 will have a minimum of 13 subjects and a maximum of 35 subjects, with the maximum occurring if and only if at least 3 subjects have an objective response in the first stage of the trial. The total minimum sample size for the trial is 27, with a maximum of 68 subjects.

The design for Cohort 1, platinum ineligible subjects, is based on a prior published ORR of 23% for atezolizumab monotherapy (Balar et al., 2017). The null hypothesis that the true ORR is 0.23 will be tested against a one-sided alternative. The null hypothesis will be rejected if 13 or more responses are observed in 33 subjects. This design yields an actual 1-sided type I error rate of 0.0244 and power of 0.7027 when the true ORR is 0.43 for the combination.

The design for Cohort 2, platinum refractory subjects who are anti-PD-L1 naïve, is based on a prior published ORR of 15% for atezolizumab monotherapy (Rosenberg et al., 2016). The null hypothesis that the true ORR is 0.15 will be tested against a one-sided alternative. The null hypothesis will be rejected if 10 or more responses are observed in 35 subjects. This design yields an actual 1-sided type I error rate of 0.0249 and power of 0.7092 when the true ORR is 0.33 for the combination.

Based on simulations with the two-stage, two-cohort design, the overall type-1 error rate will be approximately 4.7%, and the power for the trial, indicating at least one of the two cohorts will be positive given the alternative hypotheses are true, is approximately 91%.

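### The Protocol and SAP conflict on which subjects decide success once enrolment is extended to fill the EE set, so the stated type I error is not guaranteed

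*Protocol*

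**What the plan says.** **Rules that extend enrolment or replace subjects**

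- Protocol 9.12: success is declared if the FAS reaches the bar. If that is unclear, "additional subjects will be enrolled until the full sample size for Stage 2 is reached in the EE Set". The Protocol does not define *unclear*, and does not say what a full EE set then decides.
- Protocol 9.3: "Subjects who failed to meet the EE Set criteria will be replaced unless 4 or more responses in Cohort 1" (or 3 or more in Cohort 2), or unless the Stage 1 bar is out of reach even if every replacement responds. Protocol 9.7.1 and 9.11 repeat the Stage 1 extension.
- SAP 2.1, Stage 2 of Cohort 1: "If any subject is not evaluable for the primary endpoint, the subject may be replaced until a total of 33 subjects are evaluable". The same rule applies in Cohort 2, up to 35.
- SAP 2.6.4.2: after a miss on the FAS at Stage 1, the EE set may take the cohort into Stage 2 if the posterior probability of the alternative exceeds 50%.

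**Rules that tie the decision to the FAS**

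- Protocol 9.3: with surplus evaluable subjects, the primary evaluation uses the first 33 (or 35) accrued FAS subjects. EE is for sensitivity analyses.
- SAP 4.4.5.1: success rests on the FAS. If an analysis set exceeds its planned size, the bar is re-derived to hold 0.025.

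**Error rate and size.** In Protocol 9.10, "the sample size for each cohort was based on a one-sided nominal alpha of 0.025 and 70% power", and "the overall type-1 error rate will be approximately 4.7" percent. SAP 4.1 adds: "The total minimum sample size for the trial is 27, with a maximum of 68 subjects".

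**The concern.** In a single-arm trial this response-count rule is the only error control, and its error rates depend on a fixed set of subjects examined once. Here the two documents give different answers on who is counted once enrolment runs past 33 or 35: the first 33/35 FAS subjects (Protocol 9.3), a larger FAS against a re-derived bar (SAP 4.4.5.1), or 33/35 evaluable subjects after replacement (SAP 2.1).

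The trial is open label and responses are monitored continuously, so the choice could be made after the results are known. An EE set filled to exactly 33 or 35 does not exceed its planned size. The re-derivation in SAP 4.4.5.1 would therefore not touch it, and anyone who counted it would naturally apply 13/33 or 10/35.

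EE membership also depends on events after treatment starts. It requires the Week 4 prime dose, while the first scan is at about Week 10. If subjects lost before Week 4 respond less often, the EE set is enriched for response relative to the FAS.

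**Working it through.** **Inputs**

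- Cohort 1 (Protocol 9.7.1): "If there are 3 or fewer responses in these 14 subjects, the cohort will be stopped"; "The null hypothesis will be rejected if 13 or more responses are observed in 33 subjects"; null response rate 0.23, alternative 0.43.
- Cohort 2 (same section): stop at 2 or fewer of 13; reject at 10 or more of 35; null 0.15, alternative 0.33.
- q, the share of FAS subjects outside the EE set: not given in either document. Assumed 5% and 10%, with 20% to show the range.

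**1. The plan's own figures.** With Stage 1 size n1, stopping limit r1, final size n and bar R:

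P(reject) = sum over x > r1 of b(x; n1, p) × P(X2 ≥ R − x), where X2 ~ Bin(n − n1, p).

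- Cohort 1: error 0.02437, power 0.7027. Stated: 0.0244 and 0.7027.
- Cohort 2: error 0.02494, power 0.7092. Stated: 0.0249 and 0.7092.
- Trial-wide error: 1 − (1 − 0.02437)(1 − 0.02494) = 0.0487.
- Trial-wide power: 1 − (1 − 0.7027)(1 − 0.7092) = 0.9135.

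The cohort figures match one pass through one set. They contain no EE route.

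**2. Only the first 33/35 FAS subjects decide, with the SAP's Stage 1 EE route kept.** Under the Beta(1,1) prior the posterior is Beta(1 + x, 1 + n1 − x). P(p > 0.43) first passes 50% at 6 of 14, and P(p > 0.33) at 5 of 13. By simulation the errors are about 0.0244 and 0.025, trial-wide 0.049. If the Stage 1 stop were ignored altogether, the bounds are P(X ≥ 13 | 33, 0.23) = 0.0258 and P(X ≥ 10 | 35, 0.15) = 0.0292, trial-wide 1 − (1 − 0.0258)(1 − 0.0292) = 0.0542.

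**3. An EE pass at the unchanged bar also counts, with the SAP's posterior condition at Stage 1.** There were 600,000 simulated trials per cell. The FAS response rate is held at the null, and the EE set is filled to 33/35 if the FAS misses. Where non-EE subjects never respond, EE subjects respond at p0/(1 − q); at q = 10% that is 0.23/0.9 = 0.256 and 0.15/0.9 = 0.167.

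| q | Non-EE subjects respond | Cohort 1 | Cohort 2 | Trial-wide |
|---|---|---|---|---|
| 5% | equally | 0.0294 | 0.0295 | 0.058 |
| 5% | never | 0.0348 | 0.0327 | 0.066 |
| 10% | equally | 0.0325 | 0.0316 | 0.063 |
| 10% | never | 0.0499 | 0.0429 | 0.091 |
| 20% | equally | 0.0350 | 0.0352 | 0.069 |
| 20% | never | 0.1021 | 0.0743 | 0.169 |

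Repeat runs move the trial-wide figures by about 0.1 percentage point. In the *equally* rows the EE test on its own keeps about 0.024 and 0.025, so the excess comes purely from the second chance.

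**4. Surplus FAS subjects are counted.** At an unchanged bar, 13 of 36 has error 0.0469 and 10 of 39 has 0.0452. Re-deriving the bar as in SAP 4.4.5.1 gives 14 of 34–36 or 15 of 37–39 in Cohort 1, and 11 of 36–40 in Cohort 2. One test at the final size is then conservative (trial-wide about 0.034–0.035). Testing at 33/35 and again at the larger size gives 0.051–0.058 over q = 5–20%.

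**5. Trial size.** At q = 10%, filling both EE sets takes about 33/0.9 + 35/0.9 = 36.7 + 38.9 = 75.6 subjects, against a maximum of 68. This needs both cohorts to reach Stage 2 and both to be extended. Under the null, a cohort reaches Stage 2 and then misses on the FAS with probability 0.383 (Cohort 1) or 0.283 (Cohort 2), so both do so with probability 0.383 × 0.283 = 0.11.

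**The case against.** The strongest reply is that the FAS already decides. Both documents call EE a sensitivity set; Protocol 9.12 declares success only on the FAS; SAP 2.6.4.1 calls a cohort that misses on the FAS at Stage 1 not promising; and SAP 2.6.4.2 describes the later EE enrolment as being for sensitivity analyses. This stands in one important respect. A reader might infer that an EE pass rejects the null and that the plan therefore breaks its type I error. Neither document says so.

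The reply does not remove the conflict. Protocol 9.7.1 uses the EE set for the interim futility analysis, and SAP 2.6.4.2 lets it carry a cohort forward. If an EE pass can never count, the Stage 2 extension in Protocol 9.12 has no decision to serve.

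Other stronger readings also fail:

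- *Subjects outside the EE set are near-certain non-responders.* Protocol 4.2.5.1 lets one agent stop for an adverse event while the other continues, so a subject who misses the second prime may still respond. The SAP's other EE criterion, an assessable baseline scan, precedes treatment.
- *The benchmarks show that the EE set is the wrong comparison.* The Cohort 2 source is described as analysed by intention to treat, but the Cohort 1 source as 119 evaluable patients (Protocol 2.1).
- *SAP 2.1 contradicts SAP 4.3.3.* One says whether another subject may be enrolled; the other says how a withdrawn subject is scored. Both can apply to the same person.
- *The stated 4.7% is an error.* The exact 4.87% is also below 5%, and the documents call their figure approximate and simulated.

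The interim decision trees (Figure 1 in each document) are not shown in the text available, so a Stage 1 detail may be stated there.

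**Conclusion.** The concern holds as a conflict over who is counted and which set decides. The stated errors are correct for one pass on the first 33/35 FAS subjects and are not guaranteed under the extension and replacement rules.

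The size depends on the reading. If an EE pass at the unchanged bar counted, with the SAP's posterior condition applied at Stage 1, trial-wide error would be about 5.8% to 6.6% at q = 5% and 6.3% to 9.1% at q = 10%. The low end assumes that subjects outside the EE set respond equally, the high end that they never respond. If only the first 33/35 FAS subjects decide, the error stays near 4.9%; the cost is then Stage 2 patients enrolled for no decision and a possible overrun of the stated maximum.

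The arithmetic is firm. What is uncertain is q, the response rate of subjects outside the EE set, and whether the sponsor would ever count an EE pass.

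**What to change.** State in Protocol 9.3, 9.7.1, 9.11 and 9.12, and in SAP 2.1, 2.6.4 and 4.4.5.1, that:

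1. success is decided only on the first 33 (Cohort 1) and first 35 (Cohort 2) accrued FAS subjects;
2. a subject without a confirmed response counts as a non-responder, and none is replaced for this test;
3. the Stage 1 decision uses the first 14 and first 13 FAS subjects;
4. the Stage 2 extension to fill the EE set is removed;
5. EE results are reported only as a sensitivity analysis on subjects already enrolled.

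The matching sentence on Stage 1 enrolment in SAP 4.2 should follow. With the test set fixed, the bar needs no re-derivation for surplus subjects. Optionally, restate the overall type I error as about 4.9%.

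The cost is wording in both documents. Stated power (0.7027 and 0.7092) is unchanged, because it was computed for this rule. The downside is small: the EE sensitivity set may fall short of 33/35, and a cohort that misses on the FAS at Stage 1 could no longer be rescued.
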